	All subjects will be invited to one additional extended follow up visit that will occur at least 30 months after wound closure confirmation for a blinded assessment of cosmesis, function and QoL evaluation
Dosage and route of administration:	Two grams or 5 grams of NexoBrid sterile powder are mixed in 20 grams or 50 grams of sterile Gel Vehicle to obtain NexoBrid Gel. NexoBrid Gel is applied to the burn wound at a dose of 2g NexoBrid/20g Gel per 180cm² for four hours.
	In most cases, NexoBrid is effective after a single application; however it may be applied for a second time to the same burn area based on the investigator's judgment of debridement efficacy.
	NexoBrid should not be applied more than twice to the same burn wound area.
	NexoBrid should not be applied to more than 15% TBSA in one session.
	Inclusion Criteria- Patient level
	1. Stage 1: Males and females between 4 years to 18 years of age,
	Stage 2 (upon DSMB review): Males and females between 1 year to 18 years of age.
	Stage 3 (upon DSMB review): Males and females between 0 years to 18 years of age.
	2. Thermal burns caused by fire/flame, scalds or contact.
	3. Patient total burns area $\geq 1\%$ DPT and / or FT,
	4. Patient total burns area should be ≤ 30% TBSA; SPT, DPT and/or FT in depth,
Inclusion/ Exclusion Criteria:	5. Signed written informed consent by a legal guardian can be obtained within 84 hours of the burn injury.
	Inclusion Criteria - Wound level
	At least one wound (a continuous burn area which can be treated in one session; might include several anatomical areas) in a patient should meet all following criteria:
	 Wound that is ≥ 1% TBSA (DPT and/or FT) (not including face, perineal or genital),
	2. Wound is composed of DPT and/or FT in depth. Superficial partial thickness areas may be included in the wound area only if cannot be separated from deeper areas (e.g. surrounded by or mixed with DPT areas) and might interfere with the treatment of the deeper areas,
	3. Wound that is intended for surgical eschar removal,
	4. Wound's blisters can be unroofed, as judged by the investigator.

FINAL

Exclusion Criteria

- 1. Patients weighing less than 3kg,
- 2. Patients who are unable to follow study procedures and follow up period,
- 3. Patients with electrical or chemical burns,
- 4. Patient with a continuous burn area above 15% TBSA,
- 5. Patients with no DPT and/or FT burn area (only SPT wounds),

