7.1. Trial Schedule

CIDS - Protocol Code: MW2012-01-01 Page 24 of 138

Table 1: Treatment flow chart – Study Schedule (all arms)

* Weekly FU assessments will be performed 7±2 days post eschar removal and, thereafter on a weekly basis until wound closure. Long term FU will be performed 6 and 12 weeks, 6,12,18 and 24 months after last wound closure confirmation.

#-If applicable

	Screening	Pre-treatment	Treatment		Daily	Wound	Weekly FU*	Hospital	FU (weeks 6, 12
	& Baseline		NexoBrid	SoC (including	Assessments	Management &		Discharge or	months 6, 12, 18,
		- Within 1 h pre	(S=Soaking	additional		Re-admission –		premature	24)
Parameter		treatment –	R=Removal)	procedures post		surgical		discontinuation	
		Both Arms		NexoBrid)		procedures		visit	
Signing informed	Х								
consent									
Medical history	Х								
Burn Description	Х								
ConMeds & AEs	X	X	X	Х	Х	X	X	Х	X
Physical examination	Х							Х	
Demographic data	X								
Vital signs	Х				Х				
Pain assessment	X	X	4h post R	Pre and 4h post	Х				
Photograph of TWs	Х	Х	Post S	Pre & Post		Pre & post	Х		Х
Local Lab - HbA1C,	Х								
βhCG									
Central Lab:		Х	4h post R	Pre & 4h Post					
Urianalysis									

	Screening	Pre-treatment	Trea	tment	Daily	Wound	Weekly FU*	Hospital	FU (weeks 6, 12
	& Baseline		NexoBrid	SoC (including	Assessments	Management &		Discharge or	months 6, 12, 18,
		- Within 1 h pre	(S=Soaking	additional		Re-admission –		premature	24)
Parameter		treatment –	R=Removal)	procedures post		surgical		discontinuation	
		Both Arms		NexoBrid)		procedures		visit	
Central Lab:		Х	4h post R	Pre & 4h Post					
Biochemistry ²									
Central Lab:		Х	4h post R	Pre & 4h Post		Pre & post			
Hematology									
Randomization	Х								
Local Lab: Wound		Х	Post S	Pre & Post					
culture									
Local Lab: Blood		Х	4h post R	4h Post					
culture ³									
PK⁴		Х	X		Х				
Immunogenicity ⁵		Х					X		Х
Local Lab: PTT & INR		Х	4h post R	4 h post – first					
				treatment only					
Coverage				Start and end		Start and end			
				date, type of		date, type of			
				primary dressing		primary dressing			
Pressure		#	#	#1 h pre & Post					
Measurement (for									
Circumferential									

	Screening	Pre-treatment	Treat	ment	Daily	Wound	Weekly FU*	Hospital	FU (weeks 6, 12
	& Baseline		NexoBrid	SoC (including	Assessments	Management &		Discharge or	months 6, 12, 18,
		- Within 1 h pre	(S=Soaking	additional		Re-admission –		premature	24)

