Parameter		treatment –	R=Removal)	procedures post		surgical		discontinuation	
		Both Arms		NexoBrid)		procedures		visit	
extremity wounds									
monitoring)									
Cosmesis, function									Х
and quality of life ⁶									
Record of scar									X
modulating/reconstruc									
tive procedures									
Range of Motion ⁷									X
Blood transfusion	#		#	#	#	#			#
Histological biopsy	#			#	#	#	#	#	#

- 1 Physical examination will include height and weight. Height will be taken only once, at screening.
- 2 For patients weighing less than 18kg, serum chemistry will be collected at baseline only.
- 3 Blood culture is to be tested only if this is clinically indicated:
 - in patients weighing less than 18kg,
 - and/or in patients requiring two NexoBrid applications (either because of failure of the first treatment session or because >15%TBSA)
- 4 PK samples should be taken as detailed in Appendix 10 of the study protocol
- 5 Immunogenicity will be performed only for NexoBrid patients weighing at screening over 18kg at baseline, weeks 4, 8 and months 6 and 24 following wounds closure. In case that weekly visit 8 is not performed, this assessment should be taken on the relevant weekly/first follow up visit as close as possible to 8 weeks.
- 6 Cosmesis will be evaluated in donor site scars as well
- 7 Range of motion measurement of injured joints will be measured, if relevant. The measurement will be performed on the corresponding non injured joint as well, for comparison.

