7.2.3.5. Laboratory Assessments

The following tests will be performed:

Serum chemistry, hematology and urinalysis testing will be performed at a central laboratory during NexoBrid eschar removal phase. Any additional procedures require hematology tests, as described in the protocol, will be performed using Central lab. Pregnancy testing, HbA1c, wound cultures, blood cultures and biopsies (if indicated) will be performed locally on-site.

The following tests will be performed in special central laboratories: Pharmacokinetics test, Immunogenicity evaluation.

Serum Chemistry:

Urea, Creatinine, Glucose, Total Bilirubin, Cholesterol, Triglycerides, Uric Acid, Total Protein, Albumin, Globulin, Calcium (Ca++), Phosphorous, Sodium (Na+), Potassium (K+), Chloride (Cl-), Alkaline Phosphatase, SGOT (ASAT), SGPT (ALAT), LDH.

Hematology:

Hemoglobin, Hematocrit, RBC, MCV, MCH, MCHC, Platelets, Leukocyte count (WBC) with differential count.

HbA1C² will be assessed at a local lab at Screening for diabetic patients as captured during the medical history.

Statistical Analysis Plan V02 of 31 May 2021

² HbA₁C will not be collected for patients weighing less than 18kg at screening

PTT and INR will be tested at a local lab pre treatment and post treatment.

Pregnancy Testing:

A serum or urine pregnancy (β HCG) test will be performed at a local lab for women of child bearing potential.

Urinalysis:

pH, Ketone, Specific gravity, Protein, Glucose, Bilirubin, Microscopic examination.

Qualitative Wound Culture:

Test burn wound for microbial flora (swab).

Blood Culture³:

Test blood for microbial flora

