For each patient a binary (yes/no) variable will be computed indicating whether this patient had a hospital readmission or not. Additionally, for each hospital readmission, a binary (yes/no) variable will be collected indicating whether this readmission was planned or not. A readmission will be considered as being planned when the reason for readmission was indicated as "planned wound management" or "scar modulation" in the eCRF. Readmissions for which the reason was given as "AE" in the eCRF are considered as being unplanned. Hospital readmission for which the reason is given as "other" will be reviewed by the sponsor in order to decide whether they are to be classified as planned or unplanned.

Furthermore, a variable giving the number of planned hospital readmissions and a variable giving the number of unplanned readmissions will be computed for each patient.

Relative and absolute frequencies of hospital readmission (overall, planned, and unplanned) will be calculated per treatment arm.

For subjects who discontinued study participation during the efficacy assessment period, it is not known whether a(nother) readmission occurred and relevant data are missing.

Consequently, the variable is set to missing for all those subjects except for "Lost-to-follow-ups" who completed the eschar removal treatment. The exception is done under the assumption that subjects who are lost to follow up would have come back for readmission if this had been necessary (Without this exception a lot of information would have been lost in MW2010 since the percentage of subjects with re-admission is higher for "Lost-to-follow-ups" then for the rest of the population).

Change in PTT/INR

Change in PTT/INR will be computed as PTT/INR on $4h \pm 15$ min post first application (NexoBrid arm) respectively to 4h post first SoC treatment (SoC arm) minus PTT/INR pre the respective procedure for each patient.

For the classification of normal and abnormal PTT/INR values (low or high), the reference limits of the local labs will be used. If INR reference ranges will not be available for specific sites, common normal range of 0.8-1.2 will be used for these sites [19].

In addition, for each subject, for each parameter (INR/PTT) a variable will be computed, indicating whether the 4 hour post first treatment measurement was post treatment potentially clinically significant high (pCS high) or post treatment potentially clinically significant low (pCS low).

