For each of the two stages of analysis (see Section 11 for details), the safety data gathered in that stage will be analyzed separately. That is, in the first stage analysis (acute + 12M follow-up), all AEs reported until the 12 months follow-up will be analyzed separately for the following sub-periods: 1) until the 12 weeks follow-up, 2) between the 12 weeks follow-up and the 12 months follow-up (including AEs from the first sub-period that are still ongoing), 3) combined until the 12 months follow-up. In the second stage analysis (24 months follow-up), all AEs reported between the 12 months follow-up and the 24 months follow-up (including AEs from the first stage that are still ongoing) will be analyzed. Furthermore, a combined analysis, including all reported AEs, will be provided at the end of the trial.

Central Laboratory Values

For all analyses involving data from the central laboratory only samples taken within the allowed time range are considered

- Pre procedure: Within 12 hours before start of the procedure until up to 15 min after start.
- Post procedure: Within 24 hours after end of the procedure

Samples not taken in the allowed time range are excluded from the analysis.

Imputation of data from the central laboratory is only done for planned missing values. Version 10.01 of the study protocol specifies some planned missing laboratory samples. On the one hand, a laboratory sample before the additional application of NexoBrid is not required. On the other hand, a laboratory sample before a nonsurgical procedure is only prescribed for the first eschar removal procedure and a laboratory sample after a nonsurgical procedure is only

required for the last eschar removal procedure. To enable analysis of pre-post differences on procedure level, the planned missing values are imputed as follows:

- Planned missing measurements before an additional application / a non-surgical procedure
 - Values of a sample taken after the previous eschar removal procedure are used if the laboratory sample was taken within 12 hours before start of the eschar removal procedure.
- Planned missing measurements after a non-surgical procedure
 Values of a sample taken before the subsequent eschar removal procedure are used if the laboratory sample was taken within 24 hours after end of the nonsurgical procedure.

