11.1.5.14. Change in PTT/INR

Change in INR/PTT will be evaluated at 4h post first treatment. For the classification of normal and abnormal INR/PTT values, the reference limits of the local labs will be used (see also Section 10.3.4.4).

The following tables will be produced for INR and PTT:

- Shift tables indicating shifts from baseline (low/normal/high) to post first treatment (low/normal/high) as well as a listing of subjects experiencing shifts from low/normal to high
- Shift tables indicating shifts from baseline to post first treatment potentially clinically significant result as well as a listing of subjects experiencing such shifts. For the definition of pCS high and pCS low, see Section 13.2.2.

Only subjects with non-missing pre and post values will be considered for the analysis.

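### No planned INR/PTT table uses a value taken after a second NexoBrid application or session

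*SAP*

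**What the plan says.** **Analysis.** SAP 11.1.5.14: "Change in INR/PTT will be evaluated at 4h post first treatment". Both shift tables there (low/normal/high, and shift to pCS), with their listings, are defined against the value after first treatment.

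**Derivation.** SAP 10.3.4.4 (Change in PTT/INR) defines the post-treatment value at 4 h, with a 15-minute tolerance printed beside the NexoBrid arm: "min post first application (NexoBrid arm) respectively to 4h post first SoC treatment (SoC arm"). The pCS variable has the same limit, "indicating whether the 4 hour post first treatment measurement was post treatment potentially clinically significant high (pCS high").

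**Subgroups.** SAP 11.1.12.1 to 11.1.12.5 repeat the 11.1.5.14 analysis by age group without widening it.

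**Outcome.** The protocol synopsis (Safety Outcome Measures, item 4a) asks for the change in INR/PTT and how often values move above the upper limit of normal (ULN) after treatment. SAP 7.2.3.6 repeats this. Neither limits it to the first treatment.

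**Repeat exposure.** The synopsis says of NexoBrid that "it may be applied for a second time to the same burn area based on the investigator's judgment of debridement efficacy". It caps one session at 15% TBSA and admits total burns up to 30% TBSA. Footnote 3 to SAP Table 1 allows for blood culture "in patients requiring two NexoBrid applications (either because of failure of the first treatment session or because >15%TBSA").

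**Collection.** SAP 7.2.3.5: "PTT and INR will be tested at a local lab pre treatment and post treatment". In the Table 1 row "Local Lab: PTT & INR", the NexoBrid cell gives a sample 4 h after removal with no further limit. Only the SoC cell restricts sampling to the first treatment.

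**The concern.** The tabulated result is narrower than the outcome it is meant to report. It stops at first treatment, while some NexoBrid children will be exposed again. An abnormality that first appears after the second application would be missing from every INR/PTT table, and those tables would show the child's earlier, normal value.

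The SAP also treats coagulation differently from its other laboratory tests and gives no reason. The protocol words the glucose outcome almost identically to the INR/PTT outcome. Glucose is a central laboratory test, so it falls under the fuller set of tables. INR and PTT are local tests and do not. The result is a less complete coagulation safety summary for the investigational arm, in a paediatric trial.

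**Working it through.** The plan states no power, rate or precision for INR/PTT, so there is no figure to reproduce. The check compares the sections.

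**1. Which values reach a table?**

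| Analysis | INR/PTT (SAP 10.3.4.4, 11.1.5.14) | Central laboratory tests (SAP 10.3.4.4, 11.1.5.5) |
|---|---|---|
| Change from pre-treatment | First treatment only | Each procedure, and first-to-last |
| Shift, low/normal/high | First treatment only | After each procedure type including additional application, after the last procedure, and to any abnormal value |
| pCS | First treatment only | Any post-baseline value |

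Vital signs (11.1.5.6) also get a shift to any pCS result over the first 7 daily assessments. INR/PTT is the exception.

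**2. Can a child be exposed after the tabulated sample?** Yes, by either route named in footnote 3 to Table 1.
- Split sessions: session limit 15% TBSA, eligibility limit 30% TBSA. For a child treated on 30%, the first-session sample follows at most 15/30 = 50% of the treated area.
- Repeat application to the same area: the sample follows one of two applications.

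**3. Are later values collected?** Table 1 suggests so. A second NexoBrid application belongs in the NexoBrid column, where the INR/PTT cell carries no first-treatment limit. The text of 7.2.3.5 does not settle it. The only protocol text available is the synopsis, which has no sampling rule.

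**4. Worked case.** Baseline INR is 1.0 and the value after application 1 is 1.1. The value after application 2 is 1.6, which is pCS high under 13.2.2 (above 1.5 when baseline is at most 1.2). All three values are invented for illustration. The change variable is 1.1 − 1.0 = 0.1, the pCS flag is negative and no shift is recorded. The 1.6 appears in no INR/PTT table.

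**5. What could an added table show?** The documents give no rate of second applications. With 145 patients allocated 1:1, the NexoBrid arm is about 145/2 ≈ 72. The sizes k below are placeholders, about 5%, 10%, 20% and 30% of 72. They are not estimates. If the true pCS-high rate were 10% (assumed), the chance of at least one case is 1 − 0.9^k. With no cases, the one-sided 95% upper bound on the rate is 1 − 0.05^(1/k).

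| k | Chance of ≥1 case | Upper bound if none seen |
|---|---|---|
| 4 | 34% | 53% |
| 7 | 52% | 35% |
| 14 | 77% | 19% |
| 22 | 90% | 13% |

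Such a table can reveal a signal but cannot exclude one.

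**The case against.** **The first-treatment rule has a rationale.** SoC is sampled after the first treatment only, so this is the only time point with a concurrent comparator. That stands, and it is the reason to keep the existing table. It does not justify leaving later NexoBrid values out of a descriptive table.

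**Other routes may catch the event.** Coagulation events reported as adverse events after any application enter the TEAE tables (11.1.5.4). The introduction to SAP section 11 sends variables not otherwise mentioned to a case-wise listing. Both routes are real but neither is assured. The first depends on the investigator reporting a laboratory change as an event. The second covers unmentioned variables, whereas INR/PTT is mentioned and its listings in 11.1.5.14 are tied to first treatment.

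**The samples may not exist.** The evidence is one unqualified cell in a table that was damaged when read from PDF, and the plan restricts some other blood tests in children under 18 kg. This stands, so the request must be limited to values actually collected.

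**The affected group may be small.** The synopsis says one application usually suffices, and exclusion criterion 4 removes continuous burns above 15% TBSA. Both points stand, and they limit what the added table can show.

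**A worst value is not a fair comparison.** A child with two applications has more chances of an abnormal result. That also stands, and it is why the table should not be compared with SoC.

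**Conclusion.** The gap is real and modest. Every planned INR/PTT table stops at the first treatment. That is narrower than the protocol outcome and inconsistent with the SAP's own central laboratory analyses. The conclusion rests on the text of SAP 10.3.4.4, 11.1.5.14 and 11.1.12. Its practical weight depends on two things the documents do not give: how many children had more than one application or session, and whether INR/PTT was drawn after the later ones.

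Four stronger readings are not supported.
- A reader might infer that these children's coagulation data never enter the safety analysis. They contribute first-application values, and reported events are tabulated. Later values are untabulated, which differs from being counted as normal or zero.
- A reader might infer from the 15-minute tolerance that late NexoBrid samples are dropped while late SoC samples are kept. No text says so. The exclusion of off-time samples, with its window "Post procedure: Within 24 hours after end of the procedure", applies to central laboratory data, and 11.1.5.14 asks only for non-missing pre and post values. There is no basis here for importing that window.
- A reader might assume that these children have the largest exposure. One session near 15% TBSA can exceed two small applications, and that session is captured.
- A reader might put a number on the affected children. Any count would rest on an assumed rate.

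**What to change.** 1. In SAP 10.3.4.4 and 11.1.5.14, keep the post-first-treatment table and name it as the only two-arm INR/PTT comparison.
2. Add descriptive NexoBrid-arm tables for the last and the worst collected post-application INR and PTT, each against the pre-first-treatment baseline. Show shifts above ULN and pCS results under 13.2.2, split by one versus more than one application. Report how many children in each group have a value.
3. Reconcile Table 1, 7.2.3.5, 10.3.4.4 and 11.1.5.14 on whether the NexoBrid sample 4 h after removal applies to every application.

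The cost is SAP wording and a few tables on values already collected, with no new sampling requested. The added tables have no SoC counterpart, may rest on very few children, and give those with several applications more chances of an abnormal worst value. They should be labelled descriptive, with no test and no between-arm reading.

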11.1.5.15. Lower Extremity Function Scale (LEFS)

The analysis of LEFS is restricted to subjects with at least one TW with lower extremity involvement. The LEFS scores at 12 months follow up assessment will be presented by treatment group using descriptive statistics. The mean LEFS scores between treatment groups will be compared by a one-way analysis of variance.

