11.1.5.8. Blood Transfusions

The volume of blood transfusions in milliliters (as calculated in Section 10.3.4.4) will be presented by treatment group using descriptive statistics. The mean volume of blood transfusions between treatment groups will be compared by a one-way analysis of variance.

The volume of blood transfusions will be presented overall (during hospitalization), as well as separately for volumes transfused before start of treatment, during the ER period, within 1 week after the ER period and later than 1 week after the ER period.

The volume of blood transfusions will be analyzed as described above separately for calculated transfusion RBC volume, for the volume of packed red blood cells transfused and the volume of whole blood transfused.

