11.1.6.9. Duration of hospitalization

The duration of hospitalization will be analyzed descriptively with Kaplan-Meier plots and compared between groups with a log rank test.

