11.1.11. Stratification

The following factors are used to stratify the study design:

A. Age group:

A1: 0 to 23 month

A2: 24 months to 3 years

A3: 4 to 11 years

A4: 12 to 18 years

B. Overall total area of burns measured by % of TBSA

B1: (1% to 15%), inclusive

B2: (> 15% to \leq 30%)

C. The proportion of the FT area out of the total burned area of a patient

C1: < 20% of the burned area defined as FT

C2: ≥ 20% of the burned area defined as FT

D. Clinical center, so as to address possible differences in SoC procedures between sites (if any), to allow comparison of the results within center and to reduce the likelihood of a center including patients in only one arm of the study.

 $D_1, D_2,...,D_m$ (m being the number of participating clinical centers).

Using this stratification, patients will be randomized in a 1:1 ratio (NexoBrid: SoC).

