11.2.4.6. Lower Extremity Function Scale (LEFS)

The LEFS scores at 24 months follow up assessment will be presented by treatment group using descriptive statistics. The mean LEFS scores between treatment groups will be compared by a one-way analysis of variance.

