11.2.4.7. Disabilities of the Arm, Shoulder and Hand (QuickDASH)

The QuickDASH scores at 24 months follow up assessment will be presented by treatment group using descriptive statistics. The mean QuickDASH scores between treatment groups will be compared by a one-way analysis of variance.

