13.1. Randomization Algorithm

Treatment allocation is performed using the method of minimization with stratification by the factors A, B, C and D described in Section 11.1.11 above: age group (A), overall %TBSA of all TW wounds (B), overall % of FT area (C) and clinical center (D).

At any point in the trial a new patient is to be entered into the trial, the four above described factors have to be collected for that particular patient. The value for each factor of this patient is denoted by Ai, Bi, Ci and Di, respectively, where i is corresponding to the value of each factor, which is i = 1, 2, 3, 4 for factor A, i = 1, 2 for factors B and C and i = 1,..., m for factor D, with m being the number of participating clinical centers.

For example: a patient, of 25 months of age with overall total area of burns of 4% - 9% and a proportion of the FT area of ≥20% is to be recruited in the 5th clinical center. This would lead to (A2, B1, C2, D5).

The different treatment groups are denoted by j where j=1 corresponds to the NexoBrid group, j=2 to the SoC group. The numbers of patients in each stratum A, B, C, D receiving the j-th treatment and having the i-th factor are denoted by Aij, Bij, Cij and Dij.

When a new patient is to be allocated a treatment, a score for each treatment group j is determined based on the patient's specific factors and on the number of patients already allocated to the treatments. This score is denoted by Nj and is calculated by the sum of Aij, Bij, Cij and Dij. In our example the new patient has the factors A2, B1, C2, D5, hence the numbers of patients for each of these factors in treatment group j=1 which is the NexoBrid treatment are A21, B11, C21, and D51 respectively and the score N1 can be calculated as N1 = A21 + B11 + C21+D51. The score for the SoC treatment N2 can be calculated similarly: N2 = A22 + B12 +C22+D52. To determine which treatment has to be allocated to the next patient, these two scores are compared.

The trial started with the following method of treatment allocation. Since a 1:1 randomization is used in this trial, the patient is allocated to the treatment group with the smallest value among these two score values (strict minimization). Thus, the allocation decision is based on min (N1,

N2). If N1 equals N2, then simple randomization between the treatments is used with probabilities p1=p2=0.5 for each treatment.

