13.3. Update to Study Sample Size Due to COVID-19 Pandemic

According to the study protocol version 9.01 dated 29 July 2019, 160 patients were to be enrolled into the study according to the defined age group distribution. Prior to the outbreak of COVID-19 pandemic and until March 2020, 145 patients were enrolled into the study.

The COVID-19 pandemic significantly affected all study sites' ability to enroll additional patients. There was a great uncertainty regarding when restrictions would be lifted and study sites would be able to resume enrollment. Therefore, MediWound explored whether the recruitment to the study can be completed at this stage, with 145/160 (91%) of patients

enrolled, in line with FDA guidance document: "Statistical Considerations for Clinical Trials During the COVID-19 Public Health Emergency", issued on 17 June 2020.

The original sample size and statistical power calculations for this study were based on effects reached during the first Phase 3 study (MW2004-11-02) which was completed in 2009. Since then MediWound had also completed the recruitment and the 12 month follow up of 175 adult patients randomized to the Phase 3 study MW2010-03-02 (DETECT). Power calculations were performed also using data from this latest phase 3 study.

The updated sample size calculations, presented below, confirmed that based on a sample size of 145 patients, the study is sufficiently powered to meet the primary and main secondary and safety endpoints as originally planned. Thus, the study provides all required data to evaluate NexoBrid's safety and efficacy in pediatric patients while enabling the early availability of the product to address an unmet need in the pediatric population. These power calculations were submitted to the pediatric committee (PDCO) within the EMA and to the FDA to support MediWound's request for early completion of enrollment.

The request for early study completion was endorsed by the study's DSMB, relying on the confirmation that study endpoints can be met with the sample size of 145 patients and pending FDA and EMA approval.

The request for early completion of enrollment was accepted by both the FDA and the PDCO (EMA) and therefore the enrollment of patients into the study was completed with a total of 145 patients, with the following age distribution:

- 45 patients ≥0 months and ≤23 months old
- 30 patients ≥24 months and ≤3 years old
- 50 patients ≥4 years and ≤11 years old
- 20 patients ≥12 years and <18 years old

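### LEFS, QuickDASH, EQ VAS, transfusion volume and antibiotic days are compared without the minimization factors, which costs precision, and the 24-month LEFS and QuickDASH sections omit the limb restriction set at 12 months.

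*SAP*

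**What the plan says.** SAP Appendix 13.1: "Treatment allocation is performed using the method of minimization with stratification by the factors A, B, C and D". Section 11.1.11 defines the factors as age group, overall %TBSA, proportion of full-thickness area and clinical center, and adds that "patients will be randomized in a 1:1 ratio (NexoBrid: SoC"). Section 13.3 records that "the enrollment of patients into the study was completed with a total of 145 patients".

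These factors enter the models for the primary endpoint (11.1.3), the secondary endpoints (10.1.3.2, 10.1.3.3, 11.1.4), time to wound closure (11.1.5.1) and MVSS at 12 and 24 months (11.1.5.2, 11.2.4.3). Center is grouped into four regions for the primary and secondary analyses (11.1.8).

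Other safety outcomes are compared with no covariates:
- LEFS, 12 months (11.1.5.15): "The mean LEFS scores between treatment groups will be compared by a one-way analysis of variance". The 24-month section (11.2.4.6) names the same test.
- QuickDASH at both times (11.1.5.16, 11.2.4.7), and EQ VAS at both times (11.1.5.18, 11.2.4.9): also one-way ANOVA.
- Transfusion (11.1.5.8): "The mean volume of blood transfusions between treatment groups will be compared by a one-way analysis of variance".
- Days of systemic antibiotics (11.1.5.10): one-way ANOVA.

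Among the exploratory endpoints, excised area and donor-site area also get a one-way ANOVA, and hospital stay is "compared between groups with a log rank test".

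At 12 months, LEFS is limited to children with a target wound on a lower extremity, and QuickDASH to those with one on the arm, shoulder or hand. The 24-month sections begin "The LEFS scores at 24 months follow up assessment will be presented by treatment group using descriptive statistics" and "The QuickDASH scores at 24 months follow up assessment will be presented by treatment group using descriptive statistics". Neither repeats the limit or refers back to it.

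**The concern.** When allocation has been balanced on prognostic factors, an analysis that ignores them leaves their variance in the residual. The standard error is then too large and the test conservative. For a safety or function outcome that direction is unhelpful: a wide interval around a real disadvantage can be read as no difference.

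The factors plausibly matter here. Enrollment runs from birth to 18 years, and 45 + 30 = 75 of the 145 children (52%) are under four (SAP 13.3). The SAP allows for age elsewhere: the pain scale is split at age four (11.1.5.7) and EQ-5D is not assessed under age two (10.3.4.4). Transfusion is compared in raw millilitres, although the SAP's own blood-volume term is 80 mL/kg (10.3.3.2.1). That is 240 mL for a child at the 3 kg eligibility limit and 4,800 mL for a 60 kg adolescent (60 kg assumed).

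Nothing else in the SAP supplies the adjustment. The imbalance-triggered covariates in 11.1.1 serve the primary and secondary endpoints, and 11.1.5.1 extends them to wound closure. The re-randomization test covers only the main primary and secondary analyses (11.1.2).

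The missing 24-month restriction is a separate matter: the 12- and 24-month results could refer to different children.

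**Working it through.** **1. The plan's own figure.** Among the unadjusted outcomes, the SAP gives a sample size only for excised area (13.3): difference 41.85, SD 34, 90% power.

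n per group = 2(1.96 + 1.28)² × 34² / 41.85² = 13.86, rounded up to 14. This reproduces the SAP. At about 72 per arm (145/2), power at that difference exceeds 99.9%, so adjustment is immaterial for this endpoint.

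**2. Interval width, full set.** With balanced factors explaining a share R² of the variance (assumed), the width ratio unadjusted/adjusted is 1/√(1 − R²):

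| R² | Ratio |
|---|---|
| 0.2 | 1.118 |
| 0.3 | 1.195 |
| 0.4 | 1.291 |

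These are upper values, because they charge nothing for the covariates. EQ VAS has fewer than 145 children: 145 − 45 = 100, plus any infants who turned two by their first follow-up visit.

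**3. Interval width, limb subsets.** If 40-60% of children have a relevant limb wound (assumed), n is 58-87. A subset is not balanced by design, so treat the covariates as randomly balanced. With p covariates the ratio in step 2 is divided by √[(n − 3)/(n − p − 3)] and multiplied by the ratio of t quantiles on n − 2 and n − 2 − p degrees of freedom. Here p = 9 is three region terms, three for number of target wounds, age, %TBSA and full-thickness proportion; p = 6 leaves out number of target wounds.

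- n = 58, p = 9, R² = 0.2: 1.118 / √(55/46) × 0.996 = 1.02
- n = 58, p = 9, R² = 0.4: 1.291 / √(55/46) × 0.996 = 1.18

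| n | p | Excess width, R² 0.2 to 0.4 |
|---|---|---|
| 58 | 9 | 2% to 18% |
| 58 | 6 | 5% to 22% |
| 87 | 9 | 5% to 22% |
| 87 | 6 | 8% to 24% |

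Simulation of interval widths agrees to within about one percentage point.

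**4. Test size and power.** The minimization was simulated with 145 patients, the strict rule for the first 40 and then 0.9/0.1, 20 centers and a 0.5 SD difference (the 40, the 20 and the difference are assumptions; 1,000 runs per cell).

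| Set | R² | Size, unadjusted | Size, adjusted | Power, unadjusted | Power, adjusted |
|---|---|---|---|---|---|
| All 145 | 0.1 | 4.0% | 4.6% | 87% | 90% |
| All 145 | 0.3 | 2.8% | 5.1% | 88% | 94% |
| All 145 | 0.5 | 0.6% | 5.3% | 91% | 99% |
| Random half | 0.1 | 3.9% | 5.4% | 54% | 56% |
| Random half | 0.3 | 4.2% | 5.1% | 57% | 67% |
| Random half | 0.5 | 3.3% | 5.0% | 57% | 81% |

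The unadjusted test never exceeds 5% in these cells. The cost is power, and it is small when R² is small.

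**5. The 24-month population.** Let f be the share with a relevant limb wound and d the true difference among them, with no effect in other children. If everyone is scored, the observed mean difference is f × d. At f = 0.5 and d = 0.5 SD it is 0.25 SD. The restricted analysis (36 per arm) has 56% power. With all 72 per arm, power is:
- 32% if the other children have the same SD;
- 44% if their SD is half as large and their mean is shifted by 0.5 SD;
- 56%, unchanged, if they have no spread and no shift.

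The mean difference always shrinks by f; whether power falls depends on the spread among the other children.

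**The case against.** The strongest reply is that little depends on these tests. The 24-month testing is declared exploratory (11.2.8), and the protocol synopsis rests safety mainly on adverse events and laboratory abnormalities. No margin or place in the testing hierarchy attaches to these comparisons. The comparative safety outcomes that carry a margin, wound closure and MVSS, are adjusted. This stands, and it limits the weight of the point. It does not justify discarding information already collected, and the protocol does list long-term extremity function among its safety outcome measures.

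A reader might infer that function is left wholly unadjusted. It is not: range of motion is adjusted for center, %TBSA and full-thickness percentage, and the EQ-5D index for center and %TBSA. A reader might also count excised area, donor-site area and hospital stay as places where harm is hidden. All three are exploratory, the two area measures are framed as reductions in surgical need, and a conservative test of a benefit hides no harm.

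On the 24-month gap, the restriction may have been meant to carry over, and the COVID-19 memo (13.4) speaks of applicable questionnaires, so children without a limb wound may never be scored. Against that, the SAP does repeat the joint-injury restriction for range of motion at 24 months (11.2.4.8), and 10.3.4.4 puts no limb condition on collecting LEFS or QuickDASH. The text leaves the matter open.

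**Conclusion.** The point holds as a loss of precision in five safety comparisons and a gap in the wording of two 24-month sections.

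On the full set, unadjusted intervals are up to about 12-29% wider if the factors explain 20-40% of the variance. In limb subsets of 58-87 children the excess is roughly 2-24%, depending on R² and the number of covariates. R² and the limb share are assumptions; the documents give neither.

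The tempting stronger reading is that the plan biases these comparisons or conceals harm. The documents do not support it: under balanced allocation the unadjusted estimate is not biased and the test is merely conservative, and in a limb subset, where balance is weaker, the conservatism is modest. Nor do they establish that the 24-month means will be diluted. That requires children without a relevant limb wound to be scored. What is established is that, read literally, the 12- and 24-month analyses cover different populations.

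**What to change.** - For LEFS, QuickDASH, EQ VAS, transfusion volume and antibiotic days, replace the one-way ANOVA by a linear model with treatment, grouped center, age, %TBSA and full-thickness proportion. Report the adjusted difference with its 95% CI. Number of target wounds, which is in the MVSS model of 11.1.5.2, is optional in the small limb subsets.
- In 11.2.4.6 and 11.2.4.7, restate the limb-involvement restrictions of 11.1.5.15 and 11.1.5.16.
- Optionally, use a stratified log-rank test or a Cox model for hospital stay. Adjustment of excised area and donor-site area is also optional.

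The cost is SAP wording and a few model statements, with no new data. The downside is about six degrees of freedom in the limb subsets, which at low R² takes back much of the gain.
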